12.2 Methods of statistical analysis

[figure not shown]
Baseline characteristics of patients will be compared using standard univariate methods (chi-square test, t-test) to confirm the randomization was successful in achieving comparable groups. To test the primary outcome (incidence of lower GI tract paralysis), given that there may be censoring (i.e., subject may die or withdraw from study before developing lower GI tract paralysis), we will present Kaplan-Meier curves for the naloxegol and placebo groups for the time to first development of lower GI tract paralysis (≥ 3 days without a SBM after study randomization) during the ICU stay up to 10 days and compare the curves using a log-rank test. If all subjects complete the study (e.g., no deaths, no withdrawal or loss-to-follow-up for other reasons), then we will instead compare the proportion of patients that develop lower GI tract paralysis after study randomization during the ICU stay up to 10 days between the naloxegol and placebo groups using a chi-square test. The secondary outcome, time to first SBM will be estimated using a Kaplan Meier time to event analysis and compared between groups using a log-rank test. The secondary outcome of the number of ICU days without a SBM will be compared between the naloxegol and placebo groups using the Poisson regression for count data and adjusting for total number of days in the ICU (up to a maximum of 10) as an offset term in the Poisson model. The secondary outcome of the average daily opioid requirements will be compared between groups using either a student t-test or nonparametric Wilcoxon rank-sum test if the assumptions of the student t-test fail to be met. Length of mechanical ventilation and ICU stay will be reported as medians and interquartile ranges and will be compared using the Wilcoxon Rank Sum Test. For all statistical tests of hypotheses, a two-sided p-value of ≤ 0.05 will be considered as statistically significant. As this is a Phase II proof of concept study a p value of <0.10 may still be worth consideration for future study, however. All statistical analyses will be performed using SPSS 17.0. (SPSS, Chicago, IL) or other comparable commercially available statistical software.

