12.2.2 Determination of sample size

For the power analysis, the 4-day estimates of failure to defecate (i.e., failure to have a SBM) from the Kaplan-Meier plot presented in the Guardiola et. al. paper [4] was used as the estimate of lower GI tract paralysis. The figure below shows that the estimate of the percent of patients who failed to defecate (1 minus plotted proportion with defecation) by day 4 was 40% in the Prophylaxis group (i.e., the intervention group) vs. 90% in the non-prophylaxis (Treatment) group (i.e., the control group) (see yellow highlights in figure). We believe the 4-day estimate will be strongly related to the primary outcome of lower GI tract paralysis (≥ 3 days without a SBM).

90% (Placebo) vs. 40% (Prophylactic treatment), all subjects have complete follow-up, and the analysis is done using the log-rank test to compare survival curves. As sensitivity analysis, the table also shows the power of the study with this sample size under different scenarios. Because this is not the final definitive study to determine efficacy, a less stringent alpha of 0.10 may be justified for this Phase II proof-of-concept study which, if positive, would be followed by a confirmatory study [15]. While we expect most subjects to finish the study (based on the inclusion criteria), we have shown the impact on the power if approximately 20% of subjects do not finish the study. We have also varied the estimated proportion of patients failing to defecate by day 4 (i.e., not having a SBM) in the placebo group from 90% to 70% and in the prophylactic treated group from 40% to 50%.

Statistical Power of Log-Rank Test with n=18 subjects per group (36 total)

Complete study	ALPHA	Proportion Failing to Defecate at Day 4 (Placebo vs. Prophylactic Treated)				
		90% vs. 40%	90% vs. 50%	80% vs. 40%	80% vs. 50%	70% vs. 40%
100%	0.05	99.8%	98.4%	92.7%	76.0%	76.0%
	0.10	100.0%	99.4%	96.2%	84.9%	84.9%
80%	0.05	99.7%	97.6%	90.8%	72.5%	72.5%
	0.10	99.9%	99.0%	95.1%	82.2%	82.2%

For this Naloxogol randomized trial, we propose enrolling 36 subjects, 18 per group. The statistical power table below shows this sample size yields over 95% power using an alpha of 0.05 if the true day 4 estimated freedom of event (defecation) rates are

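### The primary log-rank test is swapped for a chi-square test if every subject completes: the switch is unnecessary, its branch has no stated power, and it conflicts with the sample-size section

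*SAP*

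**What the plan says.** Protocol 12.2 and SAP 12.2 carry the same text. The primary outcome is analysed as "time to first development of lower GI tract paralysis (≥ 3 days without a SBM after study randomization", with Kaplan-Meier curves "during the ICU stay up to 10 days and compare the curves using a log-rank test". The stated reason is that some subjects may be censored by death or withdrawal. The next sentence sets a condition, "If all subjects complete the study (e.g., no deaths, no withdrawal or loss-to-follow-up for other reasons", under which "then we will instead compare the proportion of patients that develop lower GI tract paralysis after study randomization" by a chi-square test over the same period. The significance rule is the same for both branches: "a two-sided p-value of ≤ 0.05 will be considered as statistically significant".

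Section 12.2.2 justifies the sample size ("we propose enrolling 36 subjects, 18 per group") from published day-4 failure-to-defecate rates: "by day 4 was 40% in the Prophylaxis group (i.e., the intervention group) vs. 90% in the non-prophylaxis (Treatment) group". Its power table is for the log-rank test throughout, including the rows with 100% of subjects complete.

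Protocol 2.1 ends the observation window at ICU discharge, death or 10 days of study drug, whichever is first.

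**The concern.** There are three problems.

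- **The switch solves nothing.** The log-rank test does not need censored data to be valid. The branch drops event timing just when timing is fully observed, and it makes the choice of primary test depend on completeness seen after randomisation.
- **Sections 12.2 and 12.2.2 disagree.** The 100%-complete rows of the power table describe a test that 12.2 says will not be run when all subjects complete. The test that would be run has no power calculation.
- **The trigger is loosely defined.** Leaving the ICU alive before day 10 is not among the named reasons for not completing. Protocol 4.1 requires only an expected stay of at least 48 hours. A patient discharged on day 2 cannot reach a 3-day event, yet the chi-square branch could count that patient as free of paralysis.

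If the branch were triggered, a real effect might be tested with less power than the plan reports.

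**Working it through.** **1. Reproduce the stated power.** Inputs from 12.2.2: 18 per arm, two-sided 0.05, 90% against 40% without defecation at day 4. Constant rates λ = −ln(S)/4 give 0.0263 and 0.2291 per day, a ratio of 8.70. Expected defecations by day 10 are 18(1 − 0.9^2.5) + 18(1 − 0.4^2.5) = 4.17 + 16.18 = 20.35. The Schoenfeld formula gives

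Φ(√(20.35/4) × ln 8.70 − 1.96) = Φ(2.92) = 99.8%,

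which matches the table.

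**2. Chi-square on the same day-4 rates.** With p̄ = 0.65,

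Φ{[√18 × 0.50 − 1.96√(2 × 0.65 × 0.35)] / √(0.09 + 0.24)} = Φ(0.799/0.574) = 91.8%.

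All five planned scenarios, alpha 0.05, complete data:

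| Placebo vs treated | Stated log-rank | Recomputed log-rank | Chi-square |
|---|---|---|---|
| 90% vs 40% | 99.8% | 99.8% | 91.8% |
| 90% vs 50% | 98.4% | 98.4% | 76.8% |
| 80% vs 40% | 92.7% | 93.2% | 70.4% |
| 80% vs 50% | 76.0% | 76.7% | 46.9% |
| 70% vs 40% | 76.0% | 68.5% | 43.7% |

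Exact Pearson power at 90% vs 40% is 92.7%, or 86% with Yates or Fisher. The last stated log-rank figure does not reproduce; it repeats the column before it. Part of the gap between the tests arises because the table models time to defecation over 10 days, not time to paralysis.

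**3. Both tests on the paralysis endpoint.** The event is the first 3-day gap without an SBM within 10 days. Trials of 18 per arm were simulated at 90% vs 40%, two-sided 0.05, with everyone followed for 10 days. The SBM rate after the first SBM is not in the documents, so it is varied as an assumption:

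| After the first SBM (assumed) | Log-rank | Chi-square | Loss, points |
|---|---|---|---|
| No later 3-day gap | 85% | 85% | 0 |
| One SBM per day | 75% | 62% | 13 |
| 0.5 SBM per day | 65% | 13% | 52 |
| Pre-first-SBM rates persist | 82% | 0.1% | about 80 |

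In the first row all events fall at day 3, so the tests agree. In the last row paralysis by day 10 is 100% vs 97.5%, which leaves the proportions almost nothing to separate. Simulated figures move by 1 to 3 points between runs.

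**4. Early discharge.** Assume exponential ICU stays, independent of bowel function, with discharge censored in the log-rank test and counted as no paralysis in the chi-square test. The documents give no discharge times.

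| Median stay | After the first SBM | Log-rank | Chi-square | Loss, points |
|---|---|---|---|---|
| 7 days | No later gap | 70% | 52% | 18 |
| 7 days | One SBM per day | 66% | 35% | 31 |
| 5 days | No later gap | 65% | 45% | 20 |
| 5 days | One SBM per day | 61% | 29% | 32 |

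Over repeat runs the 7-day losses are 18 to 20 and 30 to 33 points.

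**5. Chance of the trigger.** If each of 36 subjects fails to complete independently with probability p, all complete with probability (1 − p)^36. At the plan's 20% scenario this is 0.03%. At assumed rates of 10%, 5% and 2% it is 2%, 16% and 48%.

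**The case against.** The strongest defence has four parts.

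- **The rule is fixed in advance.** It turns on completeness, not on the treatment difference, so it gives little room to pick the favourable test. This stands. No type I error problem is shown either: the exact null rejection rate of the Pearson test at 18 per arm is 3.3% to 6.5% at the rates checked.
- **The trigger is improbable.** At 20% non-completion it is negligible. Protocol 5.6 also speaks of removing patients with no SBM at 6 days from the study, which might itself block the trigger; 5.8.1 and Appendix 1 can be read as stopping drug only. This stands, though 12.2.2 expects most subjects to finish and discharge may not count as non-completion.
- **The proportion is closer to the primary objective.** Protocol 2.1 speaks of incidence. If incidence really were 100% vs 97.5%, a non-significant comparison would be a fair answer about prevention. This stands in part. The plan has nonetheless chosen the log-rank test as its default, and which question is answered should not hinge on whether one subject is lost.
- **The list of reasons opens as examples.** Discharge could therefore be read as non-completion. This stands, so miscounting discharged patients is a possibility, not a certainty.

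A reader might infer that the switch discards nearly all power. The documents do not support that. It requires pre-first-SBM rates to persist for 10 days. Protocol section 2 reports clinicians ideally expecting at least daily SBMs after the first, and the stepped laxatives in Appendix 1 also cut against it.

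**Conclusion.** The point holds at low to moderate severity. Without further assumptions, the documents establish that the switch is unnecessary, that it makes the primary test depend on completeness after randomisation, and that 12.2.2 reports complete-data power for a test that 12.2 would not then use.

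On the day-4 rates treated as proportions, the chi-square branch would have about 92% power in the design case and 44% to 77% elsewhere. On the paralysis endpoint the loss cannot be fixed from the documents. It is none if only the first gap matters, about 13 points with one later SBM per day, about 50 at 0.5 per day, and about 80 at the extreme. If early discharges were counted as paralysis-free, an assumed 7-day median stay gives losses of about 20 points with no later gap and 30 to 33 with one SBM per day. All of this matters only if the branch is triggered, which is likely only at very low loss.

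**What to change.** In protocol 12.2 and SAP 12.2, delete the sentence that introduces the chi-square test. State that the log-rank test on time to first paralysis is the primary test in all cases, with patients discharged alive before day 10 censored at discharge. Report the proportions with paralysis in each arm descriptively. The complete-data rows in 12.2.2 would then name the same test as 12.2, although they still model time to defecation.

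The cost is one deleted sentence and one added clause. The small downside is that the simple comparison of proportions is no longer a formal test.

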2. STUDY OBJECTIVES

Given that there is no one “gold-standard” way to characterize the efficacy of naloxegol to prevent lower GI tract paralysis in critically ill adults administered scheduled opioids, given the Phase II, proof of concept nature of this investigation we plan to consider multiple outcomes to evaluate naloxegol’s efficacy in this population. Since the original April 2015 protocol submission, in an effort to help better define those outcomes that are most relevant to clinicians when they are considering the efficacy (and safety) of a preventative strategy like naloxegol in their critically ill patients at risk for lower GI tract paralysis, we informally surveyed clinicians at Tufts Med Center (and elsewhere). Of note, time to the first spontaneous bowel movement (SBM) (which is directly related to our primary outcome of prevention of lower GI tract paralysis) was suggested most frequently as the most clinically relevant outcome when evaluating a new lower GI tract paralysis prevention intervention. Clinicians noted that once a patient receiving scheduled opioid therapy has their first SBM (and remained on any particular lower GI tract prophylaxis regimen) that the patient should ideally be expected to have a SBM at least daily. Therefore, these clinicians felt that comparing the ICU days without a SBM (noting that when 3 days without a SBM is met, the definition for lower GI tract paralysis is met) was also a clinically meaningful way to compare naloxegol with placebo. While most respondents questioned whether it was necessary (or even possible) to rigidly define a SBM (e.g., based on a specific fecal output volume), they suggested that we collect the following data for each SBM [1. Stool volume (i.e., small, medium or large) and 2. Stool consistency (i.e. using the Bliss stool scale score)] Clinicians generally felt that the other outcomes that were proposed in the previous version of this protocol (for both efficacy and safety) in April 2015 were all appropriate and should all be collected given the pilot nature of this investigation. With the recently published study by Palacio de Azeda et al [13] that found that the use of an aggressive daily lactulose and enema protocol reduced the average daily SOFA (organ severity) score, and that highlighted that there may be an important connection between lower GI tract paralysis and abdominal pressure, we would like to incorporate collection of daily SOFA scores and thrice daily measurement of abdominal pressure as an efficacy outcome in the study. Lastly, a recent paper found a strong relationship between delirium and lower GI tract paralysis in the critically ill and thus we propose to monitor each subject twice daily for delirium. [12].

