2.2 Secondary objectives

To compare the efficacy of naloxegol (with placebo) in critically ill adults initiated on scheduled IV opioids on each of the following outcomes:

During the period from time of scheduled opioid therapy initiation (IV fentanyl equivalent dose \geq 100 mcg/day) until ICU discharge, death or 10 days of study drug administration (whatever comes first):

(Note: there are up to three days to enroll and randomize subject after the initiation of scheduled opioid therapy).

- a. Incidence of lower GI tract paralysis (\geq 3 days without a SBM)
- b. Time to first SBM (in hours)
- c. Days without a SBM
- d. Average daily opioid requirement [in IV fentanyl equivalents (mcg)].

Note:

1. For the purposes of inclusion in the study, only opioids administered by the IV route will be considered but to calculate the daily opioid requirement all opioids administered (regardless of route) will be considered. All enteral/oral opioids will be reduced by 50% when converting to the IV fentanyl equivalent.
2. Administration of opioids will be mandated by the ICU team (as per routine clinical practice based on the ICU team evaluation of regular pain assessment scores) and will not be protocolized as part of the study.
3. While IV fentanyl is the most common IV opioid used in the medical ICU at Tufts MC, other opioids (e.g. IV and oral hydromorphone, oral oxycodone) are used at times. Choice of opioid during routine patient care is currently not protocolized in the ICUs at Tufts MC and will not be protocolized as a part of this study. The choice and amount of opioid administered each day will be collected as part of the study.

During the period from time of study enrollment (i.e., randomization) to ICU discharge, death or 10 days of study drug administration (whatever comes first):

- e. Time to first SBM
- f. Daily characterization of each SBM for size (small, medium or large)
- g. Daily characterization of each SBM for consistency (using the Bliss Stool Scale)
- h. Daily characterization of use of the study laxative guidelines.
- i. Daily volume of enteral nutrition administered.
- j. % of daily enteral nutrition goal met.
- k. Daily fluid balance (i.e., 24 hr ins and outs)
- l. Daily maximal pain scale score (using nurse-administered 10 point rating scale)

Drug Substance: Movantik
 Study Number: ESR-15-11000
 Tufts IRB #12043
 Version: Protocol version #19
 Date: September 10, 2018

- m. Daily Sedation Assessment Scale (SAS) score
 - a. Average

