12.2 Methods of statistical analysis

Baseline characteristics of patients will be compared using standard univariate methods (chi-square test, t-test) to confirm the randomization was successful in achieving comparable groups. To test the primary outcome (incidence of lower GI tract paralysis), given that there may be censoring (i.e., subject may die or withdraw from study before developing lower GI tract paralysis), we will present Kaplan-Meier curves for the naloxegol and placebo groups for the time to first development of lower GI tract paralysis (≥ 3 days without a SBM after study randomization) during the ICU stay up to 10 days and compare the curves using a log-rank test. If all subjects complete the study (e.g., no deaths, no withdrawal or loss-to-follow-up for other reasons), then we will instead compare the proportion of patients that develop lower GI tract paralysis after study randomization during the ICU stay up to 10 days between the naloxegol and placebo groups using a chi-square test. The secondary outcome, time to first SBM will be estimated using a Kaplan Meier time to event analysis and compared between groups using a log-rank test. The secondary outcome of the number of ICU days without a SBM will be compared between the naloxegol and placebo groups using the Poisson regression for count data and adjusting for total number of days in the ICU (up to a maximum of 10) as an offset term in the Poisson model. The secondary outcome of the average daily opioid requirements will be compared between groups using either a student t-test or nonparametric Wilcoxon rank-sum test if the assumptions of the student t-test fail to be met. Length of mechanical ventilation and ICU stay will be reported as medians and interquartile ranges and will be compared using the Wilcoxon Rank Sum Test. For all statistical tests of hypotheses, a two-sided p-value of ≤ 0.05 will be considered as statistically significant. As this is a Phase II proof of concept study a p value of <0.10 may still be worth consideration for future study, however. All statistical analyses will be performed using SPSS 17.0. (SPSS, Chicago, IL) or other comparable commercially available statistical software.

[figure not shown]

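### The planned Poisson test of days without a SBM relies on a variance assumption that the outcome does not meet, so its 5% level need not hold, and the direction of the error is not known in advance.

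*SAP*

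**What the plan says.** Protocol 12.2 and SAP 12.2 carry the same text. The "number of ICU days without a SBM will be compared between the naloxegol and placebo groups using the Poisson regression for count data". The SAP gives the method in full as "Poisson regression for count data and adjusting for total number of days in the ICU (up to a maximum of 10) as an offset term", so the offset is ICU days capped at 10. Every test is judged at a two-sided 0.05, and p below 0.10 may still be carried forward to future study. No variance estimator other than the Poisson one is named. The average daily opioid requirement, by contrast, is given a nonparametric fallback if the t-test's assumptions fail.

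Three other places bear on how the count behaves:
- Protocol 2 reports the view of surveyed clinicians that after the first SBM "the patient should ideally be expected to have a SBM at least daily".
- Protocol 2.2 takes this count "During the period from time of scheduled opioid therapy initiation" "until ICU discharge, death or 10 days of study drug administration", whichever comes first, and notes that "there are up to three days to enroll and randomize subject after the initiation of scheduled opioid therapy".
- SAP 12.2.2 has a base case of 90% (placebo) against 40% (treated) with no SBM by day 4, and varies the placebo rate down to 70% and the treated rate up to 50%.

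**The concern.** Poisson standard errors assume that the variance equals the mean. This outcome is a number of days out of a known number of days, so it is bounded, and it comes in runs, because a patient who has not yet had a first SBM accumulates consecutive days without one. The bound makes the Poisson standard error too large. The clustering makes it too small. The two offset each other only by coincidence.

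Surveyed clinicians thought that this outcome "was also a clinically meaningful way to compare naloxegol with placebo". If the standard error is too large, a real effect can be missed. If it is too small, an inactive drug can look active. Either error would carry into planning of the larger trials that this study is meant to inform.

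**Working it through.** **1. The plan's own figures.** The only computed design figure is log-rank power. For 90% vs 40%, assume exponential curves over 10 days. The log hazard ratio is ln(ln 0.9 / ln 0.4) = ln(0.105/0.916) = −2.16. Expected events are 18(1 − 0.9^2.5) + 18(1 − 0.4^2.5) = 4.2 + 16.2 = 20.4. Then z = (√20.4 / 2) × 2.16 − 1.96 = 2.92, and power is 99.8%, as the table states. This supports using the day-4 rates as inputs. No power is given for the Poisson outcome, so the figure to test is the 5% level. With truly Poisson counts, the simulated planned test gives 4.6–5.0%, so the code recovers the nominal level.

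**2. Why the level moves.** Take T days, a daily probability p of no SBM, and within-patient correlation ρ:

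variance/mean = φ = (1 − p)(1 + (T − 1)ρ), and true level ≈ 2[1 − Φ(1.96/√φ)].

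With T = 10:
- p = 0.6, ρ = 0: φ = 0.40, 1.96/0.632 = 3.10, level 0.2%.
- p = 0.6, ρ = 0.3: φ = 0.4 × 3.7 = 1.48, 1.96/1.217 = 1.61, level 11%.
- p = 0.4, ρ = 0.3: φ = 0.6 × 3.7 = 2.22, 1.96/1.490 = 1.32, level 19%.

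The level is exactly 5% only when ρ = p/((1 − p)(T − 1)). At p = 0.6 that is 0.6/(0.4 × 9) = 0.17.

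**3. Null level at the plan's placebo rates.** From the documents: 18 per arm, two-sided 5%, day-4 failure 70–90%, up to three lead-in days, at most 10 study days. Assumed: lead-in uniform on 0–3 days; stays uniform on 3–10 days or fixed at 10; a later daily SBM chance of 50%, 80% or 100% (only the last comes from the clinicians' ideal); patient heterogeneity none or lognormal with SD 1; a constant first-SBM hazard calibrated to day 4. The planned test uses SE = √(1/Y₁ + 1/Y₂), where Y₁ and Y₂ are the arm totals. There were 10,000 null trials per setting.

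| Later daily SBM chance | Planned level, stays 3–10 days | Planned level, 10-day stays |
|---|---|---|
| 50% | 0.05–1.4% | 0.4–3.7% |
| 80% | 1.0–8.6% | 3.6–15.2% |
| 100% | 3.0–15.6% | 7.6–24.8% |

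Median Pearson dispersion runs from 0.25 to 2.98. HC2 on t(34), with the exact days as offset, gives 2.2–4.8%. Here the HC2 variance is the sum over arms of Σ(y − μ)²/(1 − h) divided by (Σμ)², with h = μ/Σμ. A permutation test gives 3.4–5.6% over these and the 40–50% rates.

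**4. Allowing for the laxative steps.** Appendix 1 starts laxatives at 3 days without a SBM and escalates at 4 and 5. With days 1–4 still calibrated to 70–90%, no heterogeneity, and the daily first-SBM chance raised from day 5 to assumed values, the largest planned level is about 10–11% (30% then 40%), 7.4% (40% then 50%) or about 5% (60% then 70%). Most settings fall below 5%. If counting also stops on removal at day 6, the maxima are 12.7%, 11.5% and 6.5%. HC2 stays at about 2–5% with the escalation.

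**5. Power at 90% vs 40%, no heterogeneity (planned vs HC2).**

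| Later daily SBM chance | Stays 3–10 days | 10-day stays |
|---|---|---|
| 50% | 51.7 vs 85.3% | 85.5 vs 95.6% |
| 80% | 85.0 vs 86.0% | 98.4 vs 97.0% |
| 100% | 92.8 vs 85.7% | 99.5 vs 97.4% |

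**6. Offset.** The count can span 3 + 10 = 13 days against an offset of at most 10. This moves the level by at most 0.9 points and the rate ratio by at most 0.003. At 90% failure with 10-day stays, however, the fitted placebo rate can reach 1.06 days without a SBM per ICU day, which is impossible.

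**The case against.** The best defence is that the sizes rest on quantities the documents do not give: stay length, lead-in, heterogeneity and the SBM rate after the first. That stands, which is why the results are ranges. Three stronger readings are tempting, and the documents do not support them.

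- *The test is badly inflated, up to 25%.* That needs long stays, daily SBMs after the first, and a first-SBM chance that does not respond to the laxative steps. With a strong response from day 5 and no removal at day 6, no setting at 70–90% clearly exceeds 5%. Protocol 2.1 does not count suppository-related output as a SBM, so the true response is unknown.
- *The planned test throws away a third of its power at the base case.* The loss from about 85% to 52% is the worst of six cells. One other shows a modest loss, and in four the planned test is level or ahead, partly because its own level is inflated there.
- *The 5% level definitely fails.* In a separate grid of 156 settings, 12 fell within 4–6%, 90 below 4% and 54 above 6%. It can hold by coincidence.

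It is also fair that this is one of many secondary outcomes in a 36-patient proof-of-concept study, and that the plan does not forbid a dispersion check. The plan does not say in words that it uses model-based standard errors. That is the ordinary meaning of Poisson regression when no other variance is named.

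**Conclusion.** The concern holds for the standard error and p-value of this secondary outcome. The named model does not fit a bounded, clustered day count, so its p-value can overstate or understate the evidence, and the plan gives no means of telling which. At 70–90% placebo day-4 failure, the level is about 0–25% with a constant first-SBM hazard. With a hazard that rises from day 5, its maximum is about 5–11%, slightly more if counting stops at day 6. The mismatch between mean and variance follows from how the outcome is defined. The sizes, and whether the liberal direction appears at all, depend on the stated assumptions. The offset mismatch is a minor matter of alignment. The primary log-rank test is unaffected. Severity: minor to moderate.

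**What to change.** Keep the Poisson rate ratio, but state in 12.2 that its test and interval use a small-sample robust standard error (HC2, t with 34 df). Alternatively, use a permutation test of each patient's proportion of days without a SBM. Set the offset to the log of exactly the days over which Protocol 2.2 takes the count, without the cap at 10.

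This costs one or two SAP sentences. It needs no new data and no change to the outcome or sample size, and the plan already allows other comparable software. There are two downsides. The robust test is mildly conservative (about 2–4%) when nearly all days lack a SBM. Apparent power also falls where the planned test is liberal: at 70% vs 40% with 10-day stays, daily SBMs after the first and a constant hazard, 73–77% becomes 36–45%, because the planned level there is 24–25%.
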